4.3 RATIONALE FOR ≤ 3 MONTHS POSTPARTUM

Sponsor Name: Woebot Health

Protocol Number: WB001-001

While timing of PPD indicates that the onset of a major depressive episode can occur anytime during pregnancy or within the first 4 weeks after giving birth, the protocol has specified that a woman is potentially eligible to participate in the proposed trial up to 3 months after giving birth. This 3-month period allows time for a woman to be screened for depression at their initial postpartum physical examination with their Obstetrician-Gynecologists, as recommended by ACOG and is the rational for stipulating ≤ 92 as an inclusion criterion for this study. Specifically, this initial in-person, postpartum physical exam, which is recommended standard of care practice, occurs soon after birth or within a few months after birth, depending on method of delivery. ACOG and other professional guidelines recommend screening for PPD at these postpartum visits (O'Connor et al., 2016; United States Preventative Services Taskforce, 2016). The 3-month period for the study allows women to be screened for depression or present for treatment while still maintaining alignment with the clinical definition for onset of PPD.

4.4 MINIMUM TECHNOLOGY REQUIREMENTS

Participants should have routine access to their smartphones for the duration of the trial. In order to support the study application, participants' smartphones must meet the minimum necessary operating system requirements (Apple iOS 13 and Android OS 8). In addition, they should be able to attend in-clinic and remote telemedicine visits during the trial as outlined in [Appendix 3: Schedule of Events](#).

4.5 SCREEN FAILURES

Participants who consent to participate in the clinical study but fail screening are not subsequently entered in the study. A minimal set of screen failure information is required to ensure transparent reporting of participants who fail screening, to meet the Consolidated Standards of Reporting Trials publishing requirements (Bhatt, 2022), and to respond to queries from regulatory authorities. Minimal information includes demographics, screen failure details, eligibility criteria, and any AE/SAEs. Re-screens for medication or psychotherapy stability may only be permitted with investigator approval, given all other inclusion/exclusion criteria are still met.

De-identified participant ID numbers assigned to participants who screen fail will not be reused.

4.6 STUDY DISCONTINUATION OR WITHDRAWAL

Discontinuation of study treatment for a participant occurs when study treatment is stopped earlier than the protocol planned duration and can be initiated by either the participant or the investigator. The investigator must discontinue study treatment for a given participant if he/she believes that continuation would negatively impact the participant's well-being. Involvement in the study is strictly voluntary. Participants have the right to withdraw from the study at any time for any reason, without any reprisal.

Participants should be discontinued from the study if any of the following occur:

1. The participant withdraws consent to participate in the study
2. The participant develops an illness that would interfere with her continued participation in the study
3. The participant has an SAE rated as Grade 3 (severe) or higher (see [Table 3 Clinical Concerns Categorizations](#))

Sponsor Name: Woebot Health

Protocol Number: WB001-001

4. The participant is noncompliant with treatment schedule, study procedures, in the opinion of the investigator and per the protocol, where applicable
5. The participant is confirmed to be pregnant (by self-report during scheduled assessment with the investigator/qualified site staff at Week 4 and 8)
6. The PI, Sponsor, IRB, or regulatory agency requests withdrawal of the participant
7. Any other reason relating to the participant's safety or integrity of the study data as determined by the DSMB

Participants who withdraw from the study may be replaced. Participants who withdraw or are withdrawn from the study cannot subsequently rejoin the study.

If a participant withdraws or is withdrawn from the study, the study Sponsor, sites, and DSMB will be informed immediately. If there is a medical reason for withdrawal, the participant will remain under the supervision of the investigator until satisfactory health has returned or appropriate referrals have been made and executed upon.

Unless a participant withdraws consent for follow-up procedures, they should continue to attend all scheduled study telehealth visits, including the EOT visit. Even if a participant declines to participate in the remaining scheduled telehealth visits, she will be encouraged to attend an early withdrawal visit, with the same assessments as the Week 8 EOS visit, as indicated in [Appendix 3: SoE](#).

If the participant withdraws consent for disclosure of further information, the Sponsor may retain and continue to use any collected data before such a withdrawal of consent.

Although a participant is not obliged to give a reason for withdrawing from a study, the investigator should make a reasonable effort to ascertain the reason, while fully respecting the participant's rights.

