4.7 LOST TO FOLLOW-UP

A participant will be considered lost to follow-up and withdrawn from the study if they fail to attend both scheduled key assessments visits (Week 4 and Week 8) and are unresponsive to multiple reminders and communication from the study site. Participants that miss one key assessment visit (Week 4 OR Week 8) will be permitted to continue in the study.

The following actions must be taken if a participant fails to attend a required telehealth study visit:

- The site must attempt to contact the participant and reschedule the missed visit as soon as possible, counsel the participant on the importance of maintaining the assigned visit schedule and ascertain whether the participant wishes to and/or should continue in the study.
- Before a participant is deemed lost to follow-up, the investigator or site staff designee must make every effort to regain contact with the participant, where possible. Sites will be instructed to complete at least 3 separate outreach attempts to participant via phone, text, or email (with 1 being a direct telephone call). These contact attempts should be documented in the participant's electronic case report form (eCRF) and in the EDC system.

Sponsor Name: Woebot Health

Protocol Number: WB001-001

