8.2 ANALYSIS POPULATIONS

For the purposes of analysis, the following analysis sets are defined in [Table 4](#) below.

TABLE 4. SUMMARY OF ANALYSIS SETS

Analysis Set	Description
Enrolled	All participants who signed the ICF
Intention-To-Treat (ITT)	All randomized participants with HAM-D6 measured at baseline. Participants will be included in the ITT population regardless of how often they engage with WB001 or ED001. This analysis set will be the primary set used for analyses/summaries of the primary efficacy endpoint, as well as for all secondary and exploratory efficacy endpoints.
Per-Protocol (PP)	All randomized participants also in the ITT population who complete 8 weeks of treatment and have at least 75% compliance on engaging with the Woebot application at least 1 day per week, and who have HAM-D measured at baseline, Week 4, and Week 8, with no other major protocol deviation that could affect the interpretability of the efficacy outcome. This analysis set will be used for sensitivity analyses.
Safety	All randomized participants who used WB001 or ED001 and who have at least one post-baseline safety assessment (i.e., C-SSRS). This analysis set will be used for summaries of safety data.

*Note: Inclusion criteria at screening will assess for participants engagement in TAU. If participant is confirmed as not having completed TAU by EOT, the data from these patients will be excluded from the primary analysis; however, their data will be retained for the purpose of conducting exploratory analysis.
	

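### Section 4.6 is inconsistent on whether women discontinued for noncompliance are still rated at Week 8

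*Combined protocol and SAP*

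**What the plan says.** Section 4.6 of the protocol opens with stopping the assigned app: "Discontinuation of study treatment for a participant occurs when study treatment is stopped earlier than the protocol planned duration". The only list of grounds that follows concerns leaving the study: "Participants should be discontinued from the study if any of the following occur". Item 4 on that list is "The participant is noncompliant with treatment schedule, study procedures, in the opinion of the investigator and per the protocol, where applicable". The visible text sets no threshold for it. The section then bars any woman who withdraws, or is withdrawn, from coming back, and adds: "Participants who withdraw from the study may be replaced". Further down it says: "Unless a participant withdraws consent for follow-up procedures, they should continue to attend all scheduled study telehealth visits, including the EOT visit". A woman who declines the remaining visits is to be encouraged to attend an early withdrawal visit with the Week 8 assessments.

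Three other places bear on the same women:

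- Section 4.7: "Participants that miss one key assessment visit (Week 4 OR Week 8) will be permitted to continue in the study". She counts as lost to follow-up only if she misses both key visits and does not respond to contact.
- Section 8.2, Table 4: the ITT set is every randomized woman with a baseline HAM-D6, and "Participants will be included in the ITT population regardless of how often they engage with WB001 or ED001". Compliance (at least 75%) restricts only the per-protocol set.
- Section 12.2: after an important protocol deviation, the investigator and the medical monitor agree whether the woman should be withdrawn.

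**The concern.** The primary endpoint is the between-arm difference in HAM-D6 at Week 8 in the ITT set (section 9.1). Engagement with the app happens after randomization and is partly a response to the app assigned. The two apps differ, so engagement may differ between arms. If poor engagement or missed procedures end follow-up, the Week 8 rating goes missing for a reason tied to treatment received. The primary model handles missing values under a missing-at-random assumption (section 9.8). The estimate could then drift from the effect of being assigned WB001 toward the effect in women who use it. A Week 8 rating that was never taken cannot be recovered at analysis.

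**Working it through.** The plan gives no figure on this point: no expected noncompliance rate and no count of women expected to leave under item 4. The check is mainly a comparison of texts.

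1. **Whom does the follow-up sentence cover?** Two readings fit section 4.6.
   - Reading A: it covers everyone who stops early, including women under item 4. The only exit from visits is withdrawn consent to follow-up, and noncompliance is not that. Week 8 is collected.
   - Reading B: it covers only women who stop the app, the subject of the opening paragraph. A woman discontinued from the study has left it, and Week 8 is not collected. The lead-in to the list and the bar on return point this way. Section 9.8 also plans sensitivity analyses for values lost after women leave the study early, so the plan expects such losses.

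   Nothing in section 4.6 chooses between A and B.

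2. **Does the early withdrawal visit close the gap?** Only in part. It is encouraged rather than required, and it takes place when she leaves. Appendix 3 puts it in the Week 8 column at Day 56 ±3, so a rating taken earlier is not a Week 8 rating. Section 3.4 counts a woman as a completer with baseline and Week 4 alone, so a missing Week 8 rating need not stand out.

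3. **Item 4 against section 4.7.** A missed key visit is a missed study procedure, so item 4 could apply where 4.7 lets her continue. Item 4 is limited by its reference to the protocol, and 4.7 is the protocol's specific rule for that case. This is a tension, not a flat contradiction.

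4. **Item 4 against Table 4.** ITT membership needs randomization and a baseline HAM-D6. A woman discontinued under item 4 has both and stays in the set. What can be lost is her Week 8 value.

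5. **What the model does with the gap.** The repeated measures in section 9.1 are the post-baseline visits. A woman who leaves before Week 4 with no later rating has no outcome in the model. A woman who leaves after Week 4 is in effect predicted at Week 8 from her Week 4 score and from women in her arm who stayed. That is valid only if engagement says nothing more about Week 8 once arm, baseline, Week 4 and the other covariates are known. Engagement is not a model term in the visible text. Section 9.8 adds multiple imputation and names no analysis under missing-not-at-random.

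6. **Direction, by illustration only.** Inputs: the 3-point difference of section 8.3, taken here as the effect in engaged WB001 users; an assumed share *p* of WB001 women discontinued for non-engagement; an assumed effect *e* in those women. Further assumptions: Reading B at every site, no recovery through Week 4, and no selection in the ED001 arm.

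   Effect over all randomized women = 3(1 − *p*) + *e*·*p*. Estimate from women still rated = 3. Overstatement = *p*(3 − *e*).

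   - *e* = 0 and *p* = 10%, 20%, 30%: effect 2.7, 2.4, 2.1; overstatement 0.3, 0.6, 0.9 points.
   - *e* = 1.5 and *p* = 10%, 20%, 30%: effect 2.85, 2.7, 2.55; overstatement 0.15, 0.3, 0.45 points.
   - Reading A with every woman rated: overstatement 0.

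   These figures restate their assumptions. They show the direction and are not an estimate for this trial.

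**The case against.** The strongest reply is that section 4.6 already tells sites to go on collecting data. The follow-up sentence has a single exception, withdrawn consent to follow-up, and the early withdrawal visit is a second safeguard. Data are lost only if a site disregards that sentence. This part stands: loss of Week 8 data is conditional on how sites read the section, and the plan does not prescribe it. It does not remove the inconsistency, because a site that follows the list's own lead-in is also following the protocol.

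Several stronger readings are tempting, and the documents do not support them.

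- A reader might infer that item 4 takes women out of the ITT set. Table 4 keeps them in.
- A reader might infer a direct clash with section 4.7. Item 4's qualifier leaves room for 4.7 to govern a single missed visit.
- A reader might infer that women removed under item 4 are replaced by more engaged ones. The replacement sentence refers to women who withdraw, while the next sentence separately covers those who withdraw or are withdrawn. Nothing is known about how replacements would engage, and nothing takes the replaced woman out of ITT.
- A reader might infer that sites are bound to discontinue anyone who seldom opens the app. The text says should, speaks of the treatment schedule, and relies on an investigator whom Table 2 lists as blinded. App use is a reasonable reading, because the app is the treatment. How the investigator would learn of it is not visible, and parts of section 3.5 are redacted.

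The missing-data methods also soften the risk. The model uses Week 4 with an unstructured covariance, and multiple imputation is planned. Both help less when the reason for leaving is itself related to the Week 8 outcome.

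**Conclusion.** The inconsistency within section 4.6 is real. For a noncompliant woman, one instruction ends her time in the study and another keeps her in all scheduled visits. Item 4 is also in tension with section 4.7 and with the purpose of the ITT set. The consequence is a risk: if sites read item 4 as ending follow-up, Week 8 HAM-D6 can be missing in relation to engagement, and the estimate can move toward the effect in engaged users.

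The size cannot be determined from the documents. It depends on the share of women discontinued under item 4, how many of them are still rated, how their outcome differs from that of engaged women, and how much Week 4 recovers. None of these is given. The conclusion rests on the wording alone. It justifies a correction because the correction is cheap and the outcome at risk is the primary one.

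**What to change.** Reconcile item 4 of section 4.6 with the follow-up sentence, section 4.7, Table 4 and section 12.2. Four statements would do it:

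- Noncompliance with app use or study procedures is recorded as non-adherence or as a protocol deviation. The per-protocol set already handles both.
- Noncompliance alone does not end outcome collection. The Week 4 and Week 8 HAM-D by the central rater go ahead unless the woman withdraws consent to follow-up.
- The same rule applies where section 12.2 considers withdrawal after an important deviation.
- Any replacement leaves the original participant in the ITT set.

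This concerns data collection only. The grounds for stopping treatment and the safety grounds are left to the sponsor.

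The cost is protocol wording, a site memo and some extra outreach to poorly engaged women. No visits or staff are added.

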4.7 LOST TO FOLLOW-UP

A participant will be considered lost to follow-up and withdrawn from the study if they fail to attend both scheduled key assessments visits (Week 4 and Week 8) and are unresponsive to multiple reminders and communication from the study site. Participants that miss one key assessment visit (Week 4 OR Week 8) will be permitted to continue in the study.

The following actions must be taken if a participant fails to attend a required telehealth study visit:

- The site must attempt to contact the participant and reschedule the missed visit as soon as possible, counsel the participant on the importance of maintaining the assigned visit schedule and ascertain whether the participant wishes to and/or should continue in the study.
- Before a participant is deemed lost to follow-up, the investigator or site staff designee must make every effort to regain contact with the participant, where possible. Sites will be instructed to complete at least 3 separate outreach attempts to participant via phone, text, or email (with 1 being a direct telephone call). These contact attempts should be documented in the participant's electronic case report form (eCRF) and in the EDC system.

Sponsor Name: Woebot Health

Protocol Number: WB001-001

5. DESCRIPTION OF STUDY ASSESSMENTS

Study assessments and procedures, including their timing over the 8 weeks of treatment are outlined in the SoE (see [Appendix 3](#)) and described in the subsequent subsections. Participants will be instructed to adhere to the study design schedule and to complete all required assessments and procedures. The CIR-administered HAM-D will be administered by clinical psychologists who have been appropriately trained. The Protocol Supplement (separate document) provides more detail on the specific study assessments, including response options, scoring etc.

5.1 GENERAL SCREENING/BASELINE ASSESSMENTS

After obtaining informed consent from the participant, the PI or site staff will assess the participant for eligibility as outlined in the inclusion/exclusion criteria and administer screening/base assessments (see [Appendix 3](#)). Some assessments are for screening purposes only, e.g., the Structured Clinical Interview for DSM-5 - Clinical Trials Version (SCID-5-CT).

The SCID-5-CT (First, et al., 2016) is a structured diagnostic interview for diagnosing the major psychiatric disorders found in DSM-5 that is tailored and streamlined to the primary inclusion criteria of the study. It is administered by a clinician or trained mental health professional who is familiar with the DSM-5 classification and diagnostic criteria. The interview participants may be either psychiatric or general medical patients—or individuals who do not identify themselves as patients, such as participants in a community survey of mental illness or family members of psychiatric patients. The SCID-5-CT is used in the research context to assess common disorders in mental health and will be customized for this study to specifically assess the diagnoses of major depressive disorder (MDD), current and lifetime diagnosis of a psychotic disorder including postpartum psychosis and Schizophrenia. Participants will also be assessed for bipolar disorder, homicidal or infanticidal ideation, and history of drug and/or alcohol use disorder within the past 12 months, in accordance with the inclusion criteria.

DEMOGRAPHICS

Demographic data, including year of birth/age, sex, ethnicity, and race, will be recorded.

PREVIOUS AND CONCOMITANT MEDICATIONS AND THERAPY

Previous and concomitant medications and therapy will be recorded by self-report at the time of screening/base visit and reconciled by study personnel. Any changes in medication and/or therapy would be confirmed through the study period. For this study, concomitant medications are those being taken at the time of screening or during the study.

At a minimum, concomitant medications will include all Rx drugs, standing or pro re nata (PRN) medication for dose, route, and frequency. The study will allow for exceptions of collecting common over the counter (OTCs) (e.g., ibuprofen, acetaminophen) and prescription medications (e.g., antibiotics) for minor transient ailments (i.e., non-sedating antihistamines to treat seasonal allergies or a cold). The following details must be recorded:

Sponsor Name: Woebot Health

Protocol Number: WB001-001

- Medication name (generic name)
- Reason for use
- Start and end date of administration
- The dose and frequency of administration
- Participation in psychotherapy
- The frequency of psychotherapy sessions
- Primary reason for psychotherapy

The PI should be contacted if there are any questions regarding concomitant medication.

Any changes in concomitant medications meaning a change in dose or frequency of a medication or the introduction of a new intervention or discontinuation of existing intervention will be recorded by site staff, whether the medications are for PPD, MDD, or other conditions.

MEDICAL HISTORY

Medical history, including previous and ongoing illnesses (including psychiatric), will be recorded by site staff, with the start date and end date (if applicable) of the illness or condition. Any pre-study procedures will be recorded in the eCRF as part of the medical history assessment. Any AEs that begin between the time of informed consent and the first use of the blinded study intervention will be recorded as an AE/SAE and unrelated to the device.

PREGNANCY HISTORY AND PREGNANCY STATUS

Obstetrical medical history, including total number of previous pregnancies, will be recorded by site staff in the eCRF, with applicable dates.

Although pregnancy is exclusionary and a participant who becomes pregnant during the study will be withdrawn, there are no protocol-specific requirements for pregnancy testing or contraceptive use. Changes in pregnancy status will be completed via self-report during key assessment visits. There are no precautions regarding breastfeeding during the study because the intervention is not a medicinal product.

5.2 EFFICACY ASSESSMENTS

The following table summarizes the efficacy and safety assessments that will be used for primary, secondary, and exploratory endpoints during the study period.

Assessment	Endpoint Type	Definition
HAM-D	Primary	
 The HAM-D17 is a 17-item clinician-rated measure of depression (Hamilton, 1960). The HAM-D6 is a subset of the HAM-D17 that assesses 6 core items associated with major depression: depressed mood (item 1), feeling of guilt (item 2), difficulty performing work and activities (item 7), motor retardation (item 8), psychic anxiety (item 10), and somatic symptoms (general, i.e., low energy and bodily pain) (item 13) Item 13 is scored 0 to 2 (0 = none/absent to 2 = most severe) and all other items are scored 0 to 4 (0 = none/absent to 4 = most severe). Total score ranges from 0 to 22 and a higher score indicates greater severity of depression. The HAM-D is commonly used for diagnostic purposes in research, and structured clinical interviews such as this are recommended to formally diagnose clinical depression (Norhayati et al., 2015). The HAM-D17 will be administered at baseline via the Structured Interview Guide for the Hamilton Depression Rating Scale (SIGH-D 17-item HAM-D), at Week 4, and Week 8 to derive HAM-D6
EPDS	Secondary	
 A brief self-report questionnaire used as a screening tool to identify patients who are at risk for perinatal depression (Cox et al., 1987; Wisner et al., 1994). The 10-item scale assesses depression criteria (including anhedonia, anxiety, sleep disturbance, and suicidal ideation) in the past seven days. Each item has four ordinal response options, yielding a total score of 0 to 30 where a higher score denotes greater depression (values ≥ 10 denote possible depression). The EPDS is a widely used measure with demonstrated reliability and validity for the assessment of depression (Yawn et al., 2009; Zhong et al., 2014), and is also routinely used in clinical care practice for the assessment of patients with PPD. The EPDS will be administered at baseline, Week 4, and Week 8.

PHQ-9	Secondary	
 ● A 9-item, self-report questionnaire that evaluates frequency and severity of depression symptoms within the previous 2 weeks. ● The 9 items are based on the DSM-4 criteria for major depressive disorders (American Psychiatric Association, 2000). ● Each item is scored on a 4-point Likert scale from 0 (not at all) to 3 (nearly every day). ● It is a widely used self-report measure; it has demonstrated reliability and sensitivity to clinical change. ● Scores of 5, 10, 15, and 20 represent cut points for mild, moderate, moderately severe, and severe depression, respectively (Kroenke & Spitzer, 2002). ● The PHQ-9 will be administered at baseline, Week 4, and Week 8.
GAD-7	Secondary	
 ● This is a 7-item, self-report questionnaire for assessing how often respondents have been bothered by anxiety symptoms over the last two weeks (Spitzer et al., 2006). ● Each item has 4 ordinal response categories: Not at all (0); Several days (1); More than half the days (2); Nearly every day (3). Responses are summed to yield a score from 0-21, where higher scores denote greater anxiety ● Scores of 5, 10, and 15, represent cut points for mild, moderate, and severe anxiety, respectively (Spitzer et al., 2006). ● It has demonstrated reliability, validity, and responsiveness (Dear et al., 2011). ● The GAD-7 will be administered at baseline, Week 4, and Week 8.
MIBS	Secondary	
 ● A self-report questionnaire consisting of 8 words such as “loving,” “joyful,” or “disappointed.” ● Mother’s rate each of the 8 words using a 4-point Likert scale (very much, a lot, a little, or not at all) to indicate how they feel about their baby in the first few weeks. ● Five of the words describe negative emotional responses and are reverse scored (Taylor et al., 2005). ● Total scores can range from 0 to 24, with lower scores indicating good bonding. ● The MIBS will be administered at baseline, Week 4, and Week 8.

Sponsor Name: Woebot Health

Protocol Number: WB001-001

CGI-S	Exploratory	
• A single item, 7-point Likert scale to measure the overall severity of the patient's current clinical presentation and symptomatology. (Busner et al., 2007)• The investigator will rate the participant's severity of illness based on clinical interviews and assessments relative to their experience with other patients with the same diagnosis.• Response choices include 0 (not assessed) and range from 1 (Normal, not at all ill) to 7 (Among the most extremely ill patients).• The CGI-S will be administered at baseline, Week 4, and Week 8.
CGI-I	Exploratory	
• A single item, 7-point Likert scale to measure the overall improvement in the patient's condition at the end of treatment. (Busner et al., 2007)• The investigator will rate whether the participant's total improvement was due entirely to the intervention.• Response choices include 0 (not assessed) and range from 1 (very much improved) to 7 (very much worse).• The CGI-I will be administered at Week 4 and Week 8.
PGI	Exploratory	
• The Patient Global Impression scale (PGI), also known as Subject Global Impression (SGI), is the PRO counterpart to the Clinical Global Impressions scale, (CGI), which was published in 1976 by the National Institute of Mental Health (US). (Snyder et al., 2020)• Consists of one item based on the CGI and is adapted to the patient.• The PGI mainly measures change in clinical status (PGI-C) but can also measure disease severity (PGI-S) or disease improvement (PGI-I).• PGI-S is administered at baseline, Week 4, and Week 8; PGI-C is only administered at Week 4 and Week 8.
Client Satisfaction Questionnaire	Other/ Exploratory	
• Participants will be prompted to complete an 8-question Client Satisfaction Questionnaire (CSQ) to assess their level of satisfaction with WB001 vs. ED001 applications.• The CSQ will be administered at Week 8.

